2.3 POTENTIAL RISKS AND BENEFITS

The risk profile of the Rinovum Subsidiary 2 SUI device is considered to be low. Risks to participants in this study are comparable to those routinely encountered with using vaginal

³ Ziv E, Stanton SL, Abarbenel J. Efficacy and safety of a novel disposable intravaginal device for treating stress urinary incontinence. *Am J Obstet Gynecol* 2008; 198:594.e1 – 594.e7.

pessaries. The study presents no more than minimal risk of harm to participants and involves no procedures for which written consent is normally required outside of the research context with a Class II device.

Potential risks include the following short-term risks:

- Sensitivity to the materials used in the device; however, the probability is low due to the design specification.
- Injury if the user does not understand the instructions for use. Prior to the pivotal study, label comprehension and simulated use testing will occur to refine the labelling and demonstrate safety to proceed with the pivotal study
- Irritation to the vaginal area
- Vaginal bleeding/spotting
- Urinary Tract Infection (UTI)
- Vaginal infection
- Urine Retention
- Infection if the device is not used as indicated. For example, reuse of the device could put the user at risk of infection. Instructions for use will include details regarding single, disposable use of the device and the specifications will preclude reuse by design.
- Confidentiality

There are no known long-term risks associated with this study.

This study is a non-significant risk study. The device is not intended as an implant or for use in supporting or sustaining human life. The device is intended to treat by assisting with management of the symptoms associated with a disease (Stress Urinary Incontinence). Due to the low risk profile associated with the Rinovum Subsidiary 2 SUI device, as well as other similar devices, it does not present serious risk to the health, safety, or welfare of a subject.

The materials used in the manufacturing of this device are medical-grade. During the screening process, a pregnancy test, vaginal examination and urinalysis will be performed to rule out a pregnancy, vaginal infection, or UTI, respectively. The device will be tested the screening visit to ensure fit, comfort and ability to urinate while wearing the device. A vaginal swab will be collected to establish baseline vaginal microflora, but will not be used for determining eligibility to enroll. Participants' most recent Pap smear within 36 months must be normal. Each of the participants will receive an identification number during enrollment. This number will be the only identifying factor on the CRF/questionnaire. The PI will maintain the participant information in a secure location. The Sponsor shall have access to the study data after it has been de-identified to analyze the data to determine success of the study.

Each of the devices used in this study will be labeled "Caution: Investigational device. Limited by United States law to investigational use". Additionally, each device will have a specific lot number.

Patient's undergoing successful intravaginal pessary treatment for SUI have been shown to have improvement in quality of life, so long as the device is being used. The quality of life improvement seen in patients undergoing successful SUI treatment include physical mitigation of symptoms which result in potential social effects, psychological effects and decrease in activity.

Non-surgical treatment options are important to the subject population. SUI device interventions that demonstrate efficacy and safety could significantly improve the quality of life for a condition that most patients do not like to discuss, even with their physicians. Surgical options are typically used as a last resort, so the RS-2 SUI pessary device could provide a bridge to surgery option for

patients. For this reason, the potential benefits associated with this study outweigh the risks involved.

The potential benefits to participants during this study include increased quality of life, increased social activity (including exercise), psychological improvement, and increased confidence due to decreased urinary leakage.

3 OBJECTIVES AND PURPOSE

This study is an interventional, open label, clinical study. The purpose of this study is to evaluate the efficacy and safety of the Rinovum Subsidiary 2, LLC disposable SUI pessary device. Specifically, this study will evaluate the effectiveness of the pessary device by assessing reduction in urine leakage in approximately 50 women with Stress Urinary Incontinence (SUI). Efficacy will be assessed by the reduction in mean pad weight gain per hour, reduction in the mean number of stress urinary incontinence events per day, and a quality of life questionnaire. Primary Objective is to demonstrate effectiveness of device usage. Important Secondary Objectives include demonstrating that the device reduces episodes of incontinence, improves quality of life, and is safe for over-the-counter (OTC) use. The safety will be evaluated by assessing all adverse events, including the results of urinalysis, vaginal swab, and vaginal examination.

4 STUDY DESIGN AND ENDPOINTS

4.1 DESCRIPTION OF THE STUDY DESIGN

60 to 70 women having diagnosed stress urinary incontinence (SUI) will be recruited from multiple study sites and the general population, while approximately 50 women will be included in the Per Protocol population. The participants will wear preweighed pads for 7 consecutive days during the non-treatment (control) phase. Participants will then use the device for 14 consecutive days during the treatment phase. During enrollment, before treatment phase and after treatment phase, a vaginal swab will be collected to determine any changes in the vaginal microflora of the participant.

4.2 ANALYSIS POPULATIONS

Intent to Treat Population (ITT): Any subject enrolled who gets a pre-weighed pad for the control phase. This is expected to be 60-70 subjects.

Modified Intent to Treat Population (mITT): Any subject enrolled who gets through the control phase, is given the device and pads for the treatment period, and who uses the device such that there is at least one data point to analyze - i.e., use of the pad for at least one hour during the last 7 days of the treatment period. A subject who is not in the study at the beginning of the last 7 days of the treatment period is in the ITT population but not the mITT population. The mITT is the population the analysis will be done on.

Per Protocol Population (PP): Any subject getting through the entire treatment period and has complete data (i.e., pad weight reduction data for the last 7 days of the treatment period). For example, someone having only data for 6 out of the last 7 days of the treatment period is in the mITT population but not the PP population.

Safety Population (SP): Same as ITT.

4.3 STUDY ENDPOINTS

The primary endpoint is the percentage reduction in mean pad weight gain per hour of >50% during the 14-day treatment phase versus the 7-day baseline phase. The PWG percentage reduction will be calculated by comparing the mean PWG over the 7-day baseline non-treatment phase with the last 7 days of the 14-day treatment phase for each individual participant.

Important secondary endpoints will be measured based on anecdotal evidence or feedback from the subjects. These secondary endpoints are as follows:

- (1) Reduction in mean number of SUI episodes per day from episodes from the 7-day baseline period to the last 7 days of the 14-day device treatment period as measured as reduction (improvement) in stress urinary incontinence episodes. Participants will record SUI episodes in the Study Diary during the baseline (7 days) and treatment (14 days). Negative values are indicative of efficacious outcome.
- (2) Change in Quality of Life as Measured by the ICIQ-LUTSqol Quality of Life Questionnaire.

The Quality of Life Questionnaire to be performed at baseline, before and after treatment phase of the study is based on 20 questions referring to areas which may have been influenced or changed by accidental urine loss and/or prolapse. These questions are assigned a value of, 1 = 'Not at all,' 2= 'Slightly,' 3 = 'Moderately,' or 4 'A lot.' Each area of changed is then assessed on a scale of 1-10 to see how much it bothers them. The Questionnaire is scored by taking the average score of items and then multiplying the average by 25 to put scores on a scale from 0 to 100. A lower score is considered less impact to quality of life and a higher score reflects more impact to quality of life. In the same manner, a reduction in scores from baseline reflects improved quality of life. A reduction on score of ≥ 3.7 is considered the Minimum Clinically Important Difference.

- (3) Evaluation of Adverse Event assessments to determine device is safe for use.

Important Exploratory Endpoints are as follows:

- (1) Participants can successfully use the device in accordance with the given Instructions for Use.
- (2) Participants will find the device comfortable enough to demonstrate compliance with the study procedures during the device treatment phase.

5 STUDY ENROLLMENT AND WITHDRAWAL

5.1 PARTICIPANT INCLUSION CRITERIA

Inclusion Criteria: To be eligible to participate in this study, an individual must meet all of the following criteria:

- Provision of signed and dated informed consent form
- Literacy must be in English (able to read and understand Informed Consent)
- Stated willingness to comply with all study procedures and availability for the duration of the study
- Female, aged >18

- Be in generally good health as determined by the Investigator
- Have a physician diagnosis of SUI that occurred prior to or during the screening visit of this study
- Have a \geq 3-month history of experiencing > 3 episodes of SUI per week
- Be willing to use the investigational pessary device for the control of urinary incontinence
- Have experience with wearing a tampon
- Have normal PAP smear results within the last 36 months, if applicable.

5.2 PARTICIPANT EXCLUSION CRITERIA

Exclusion Criteria: An individual who meets any of the following criteria will be excluded from participation in this study:

- Is pregnant, or planning to become pregnant during the study
- Has been physician diagnosed with urge urinary incontinence or mixed urinary incontinence prior to or during the screening visit for this study
- Is post-partum within 3 months
- Has had an intrauterine device (IUD) placement of less than 6 months
- Has self-reported difficulty emptying her bladder;
- Has a history of Toxic Shock Syndrome (TSS) or symptoms consistent with TSS;
- Has experienced difficulty inserting or wearing an intra-vaginal device, including a tampon;
- Has had vaginal surgery, perineal surgery, uterine surgery, or abortion (spontaneous or induced) within the past 3 months;
- Has any Screening laboratory value outside the laboratory reference range considered clinically significant by the Investigator which could impact the safety of the participant or the outcome of the study
- Has an active urinary tract infection or vaginal infection requiring treatment
- If for any reason, the Investigator decides that the participant should not participate in the study.
- Class III Obesity ($BMI \geq 40.0 \text{ kg/m}^2$)
- Advanced prolapse
- Fit assessment is not successful during screening visit

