Total N: Obtain informed consent. Screen potential participants by inclusion and exclusion criteria; obtain and document medical history. Confirm that participant symptoms indicate SUI diagnosis. Perform the urine pregnancy test (if applicable), urinalysis, vaginal examination and symptom evaluation to ensure participant has no active urinary or vaginal infection requiring treatment. A vaginal swab will be performed to establish baseline vaginal microflora. Perform usability and fit assessment test.

NOTE: Results of the SUI diagnosis assessment and fit assessment may deem participant ineligible for enrollment due to urge incontinence or mixed (stress and urge) incontinence diagnosis or poor /improper fit. To simulate OTC use, participants will be asked to perform self-selection and assess fit based on the product labeling prior to confirmation by the PI.

Enrollment/Visit 1 Time Point

Total N: Complete a questionnaire by the physician. Participant will also complete a baseline Quality of Life Questionnaire.

Participant will receive 14 preweighed pads to take home. Participant will perform control phase of study wearing pads for 12 hours/day for 7 consecutive days. Pads will be returned by participant for weighing and data collection.

NOTE: Results of the laboratory tests from the screening visit (pregnancy test, vaginal examination and urinalysis test) may deem a participant ineligible for enrollment due to positive pregnancy result, positive vaginal infection requiring treatment, or positive urinary infection requiring treatment, respectively.

Visit 2 Time Point

Total N: Urine pregnancy test, if applicable, to rule out pregnancy, vaginal examination, and symptom evaluation will be repeated to rule out any potential infection requiring treatment. Vaginal swab will also be repeated to evaluate changes in vaginal microflora. Quality of Life questionnaire will be repeated. Participants will be given 20 study devices and 28 preweighed pads to perform the treatment phase of the study. Participants will wear 14 devices and 14 pads simultaneously for 14 consecutive days. Pads will be returned by participant for weighing and data collection, and participants will record information regarding activity level and quality of life.

Visit 3 Time Point

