2.2 RATIONALE

This study is an interventional, open label, single-arm, clinical study in which participants will serve as their own controls. This study will enroll participants deemed eligible per the Inclusion/Exclusion Criteria. This study will evaluate the safety and effectiveness of the Rinovum Subsidiary 2 (RS-2) SUI pessary device by assessing reduction in urine leakage in approximately 50 women with SUI. Efficacy will be assessed by reduction in pad weight gain, frequency of stress urinary incontinence events, and a quality of life questionnaire. The study design consists of a control/no treatment period for each subject and a device treatment period for each subject.

The participants in this study will use the pre-weighed pads daily for 12 hours per day to obtain baseline control urine leakage data. This baseline will be for 7 consecutive days. The pads may be changed as necessary during this time. The same participants will use the device, and the same pre-weighed pad method for 14 consecutive days during the treatment period. Participants will be asked to schedule the treatment phase during a time when they will not have an interruption in the treatment phase such as menstrual cycle or travel. Patients will be asked to perform the treatment period within 21 days. In both the non-treatment and treatment phase of the study, the preweighed pads will be collected and weighed for use in calculating pad weight gain (PWG).

Safety analysis will include results of urinalysis, vaginal swab, vaginal examination, and evaluation of adverse events.

Usability of the device will be assessed by the PI at Enrollment where the participant will insert the device while following the Instructions for Use. The PI will examine the device inside the vagina to ensure successful placement and fit.

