7.3 STUDY SCHEDULE

Prior to enrollment, screening questions, a medical file review, a physical examination, pregnancy test (if applicable), urinalysis, and a human factors and a fit assessment will be used to determine/assess whether a participant meets the eligibility criteria. A vaginal swab shall be performed to establish baseline vaginal microflora. These activities must be performed within 1 week of enrollment. Informed consent will be obtained prior to any screening procedures. The human factors and fit assessment will include the following:

- Participant will perform self-insertion and removal in accordance with the IFU under supervision of physician
- Participant will provide feedback regarding the fit of the device based on the IFU description of proper fit without input of the physician
- Physician will verify device is a proper fit for participant after participant performs self-insertion (if physician determines the device is not a good fit for the participant, the participant may be terminated from the study)

Enrollment/Visit #1 schedule shall consist of the following:

- Provide participants with a description of what to expect with the study
- Participant will complete a Quality of Life Survey
- Provide the patient with a Baseline Study Diary for them to keep track of their leaking patterns for the first phase of the study
- Physician will administer 14 preweighed pads for the patient to wear for 7 consecutive days.
- Record any adverse events

NOTE: all worn pads will be placed in preweighed, double sealed, ziplock bags and returned to the clinical site via mail within 48 hours of use by the participant for weighing throughout the entirety of the study

NOTE: to minimize time between pad wearing and pad weighing, participants will be mailing back all worn pads immediately upon completion of the 7-day wear to the site. The site will record the pad weights in the Pad Weight Log form.

Visit #2 schedule shall consist of the following:

- Update Medical History, if applicable
- Perform a urine pregnancy test, if applicable
- Perform a vaginal swab for vaginal microflora assessment
- Assess for any symptoms of active vaginal infections requiring treatment (if a patient is symptomatic of a vaginal infection, they may be treated and enrolled at a later date once vaginal infection has resolved).
- Collect Baseline Study Diary from participant
- Go over a series of questions with participants
- Repeat the Quality of Life questionnaire

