10 STATISTICAL CONSIDERATIONS

10.1 Populations

Intent to Treat Population (ITT): Any subject enrolled who gets a pre-weighed pad for the control phase. This is expected to be 60-70 subjects.

Modified Intent to Treat Population (mITT): Any subject enrolled who gets through the control phase, is given the device and pads for the treatment period, and who uses the device such that there is at least one data point to analyze - i.e., use of the pad for at least one hour during the last 7 days of the treatment period. A subject who is not in the study at the beginning of the last 7 days of the treatment period is in the ITT population but not the mITT population. **THE mITT IS THE POPULATION THE ANALYSIS WILL BE DONE ON.**

Per Protocol Population (PP): Any subject getting through the entire treatment period and has complete data (i.e., pad weight reduction data for the last 7 days of the treatment period). For example, someone having only data for 6 out of the last 7 days of the treatment period is in the mITT population but not the PP population.

Safety Population (SP): Same as ITT.

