- b. For the quality of life score there will be three measures as described in the visit schedule above. For descriptive purposes the results and change from the previous visit will be shown, as well as the change from the enrollment visit to the post-treatment visit. The changes will likely be negative scores as the QOL is expected to improve, as the instrument records lower numbers as indicating a better quality of life. For the purposes of inferential analysis, a mixed model analysis of variance on the scores will be used on the result at time t (t=baseline, post-control, post-treatment) with time as a fixed effect and subject as a random effect. Thus, the null hypothesis is that there is no significant difference from baseline/enrollment to post-treatment, i.e., that the mean change in score is 0. The alternative is that this change is less than 0. Correlation of scores within subjects will be considered as compound symmetric. The p-value indicating the significance of the least square mean score at the third time-point compared to that at the first time-point will determine if the endpoint is met.

All inferential testing will be done on the mITT population and will be one-sided. As noted above statistical significance will be reached if the relevant p-value is less than 0.0167. Results for all populations will be reported.

There is a secondary safety endpoint as described earlier in the protocol. Safety reporting using urinalysis, vaginal swab, vaginal examination, and evaluation will be descriptive and narrative in nature.

Similarly, exploratory endpoint results of comfort and successful use will be descriptive. No inferential hypotheses will be used here.

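### A successful-use rate in enrolled women leaves out those who failed the screening insertion and fit test, so it cannot alone estimate success in unscreened over-the-counter users

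*Combined protocol and SAP*

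**What the plan says.** **The endpoint.** Section 4.3 lists as exploratory that "Participants can successfully use the device in accordance with the given Instructions for Use". It does not say what counts as success, when it is judged, or in whom. Section 10.4 adds that "exploratory endpoint results of comfort and successful use will be descriptive", and Section 10.6 leaves the details to the SAP.

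**The test.** Section 7.3 describes the human factors and fit assessment: "Participant will perform self-insertion and removal in accordance with the IFU under supervision of physician". The woman then judges the fit herself and the physician verifies it. The schedule table in Section 7.3 places this assessment at Screening and at no later visit. The Schematic of Study Design gives the purpose as simulating OTC use: "participants will be asked to perform self-selection and assess fit based on the product labeling prior to confirmation by the PI". Section 2.2 describes what appears to be the same procedure but places it at another time: "Usability of the device will be assessed by the PI at Enrollment where the participant will insert the device while following the Instructions for Use".

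**Entry gate.** Section 5.2 lists as an exclusion "Fit assessment is not successful during screening visit". Section 7.3 is softer: it permits, but does not require, ending participation when the physician finds a poor fit.

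**The populations.** Sections 4.2 and 10.1 define the ITT population, which is also the Safety population, as "Any subject enrolled who gets a pre-weighed pad for the control phase". The mITT and PP populations are narrower. Section 10.4 says "Results for all populations will be reported". No screened or fit-tested population is defined.

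**The concern.** The same test serves as the usability observation and as the entry criterion. A woman who fails it under Section 5.2 is never enrolled and so belongs to no analysis population. A rate computed in any of the four populations is therefore conditional on having passed.

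This matters because safety for OTC use is a stated secondary objective and the device comes in one size (Section 6.1). An important OTC error is a woman who accepts a fit that a physician would reject, since a retail buyer has no physician to stop her. The screening test can observe that error. If Section 5.2 is applied, every enrolled woman has a physician verdict of acceptable fit, so this kind of disagreement cannot appear in the enrolled data. Two further criteria select in the same direction: tampon experience is required (Section 5.1), and earlier difficulty with an intravaginal device is excluded (Section 5.2).

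**Working it through.** The plan states no figure for this endpoint, so there is none to reproduce. Table 1 in Section 10.3 concerns the primary endpoint and is not an input here.

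**Inputs from the documents.** 60-80 women screened (Section 5.3); 60-70 enrolled (Section 10.3). No fit-failure rate and no expected usability rate are given, so both are assumptions below.

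**Reading 1: the endpoint is the supervised test.** Let E be the number enrolled and F the number failing the fit test. With Section 5.2 applied, the rate in enrolled women is E/E and the rate in all women tested is E/(E + F). Intervals are exact (Clopper-Pearson) 95%.

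| E | F (assumed) | Enrolled only | All tested |
|---|---|---|---|
| 60 | 0 | 60/60 = 100% (94.0-100) | 60/60 = 100% (94.0-100) |
| 60 | 5 | 100% (94.0-100) | 60/65 = 92.3% (83.0-97.5) |
| 60 | 10 | 100% (94.0-100) | 60/70 = 85.7% (75.3-92.9) |
| 60 | 20 | 100% (94.0-100) | 60/80 = 75.0% (64.1-84.0) |
| 70 | 10 | 70/70 = 100% (94.9-100) | 70/80 = 87.5% (78.2-93.8) |

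F = 20 is the most that 80 screened and 60 enrolled allow (80 - 60). With 70 enrolled the most is 80 - 70 = 10. These maxima count every non-enrolled woman as tested and failed on fit. A woman who passed the fit test but was excluded for another reason would add one to both numerator and denominator and raise the rate.

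**Reading 2: the endpoint is home use over 14 days.** Passing one supervised test does not fix this rate. Let u be home success among E = 60, and count fit failures as non-successes. The rate is u in enrolled women and 60u/(60 + F) in all women tested.

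- u = 80%: 48/60 = 80% in enrolled women; 48/80 = 60% of all tested with F = 20, and 80% with F = 0.
- u = 95%: 57/60 = 95% in enrolled women; 57/80 = 71% of all tested with F = 20, and 95% with F = 0.

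On either reading the two denominators agree only when F = 0. Whether F is small cannot be learned from the enrolled women.

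**The case against.** - **The endpoint may not be the screening test.** Section 4.3 gives no time point, the companion exploratory endpoint concerns the treatment phase, and Visit 3 collects a treatment diary and a final questionnaire. A reader might infer that the usability rate is close to 100% by construction. That follows only under Reading 1, and the documents do not settle which reading applies. Reading 2 still omits the women who failed at entry.
- **No population is assigned to this endpoint.** Restriction to enrolled women is an inference from the population definitions and from Section 10.4. Section 10.2 promises listings of all case report form data. This stands, but a listing is not a summary, and screen failures are not mentioned.
- **The gate may leak.** Under the permissive wording in Section 7.3, some poor-fit women could stay in. A woman who wrongly thinks the fit is poor, but whom the physician passes, is not excluded on this criterion. Both points stand.
- **Fit failure is not the same as user failure.** The test also covers comfort and the ability to void (Sections 2.3 and 7), so a woman can follow the instructions correctly and still fail. This stands, and it is why reasons must be tabulated separately.
- **Few non-enrolled women may be fit failures.** Section 5.2 has 13 other exclusions. This stands, so the low end of the range is an extreme.
- **Other OTC evidence exists.** Participants get the instructions and no training (Section 6.1), and label-comprehension and simulated-use testing precede the study (Section 2.3). A reader might infer that the study cannot support OTC use. The documents do not bear that out: no OTC threshold hangs on this endpoint, and the labeling claims in Section 10.4 rest on the primary and two secondary endpoints.

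**Conclusion.** The point holds in a limited form. As planned, a successful-use rate in the defined populations is conditional on passing the only scheduled observed-use test. It is near 100% by selection if the endpoint is that test, and selected upward if it is home use. It cannot by itself estimate success among unscreened OTC users.

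The size is uncertain. Success among all women tested could lie anywhere from 75% to 100%, given the planned screening and enrollment numbers and no stated fit-failure rate. A reader might take 75-88% (60/80 to 70/80) as the expected result. The documents do not support that, because it assumes 80 women tested and every non-enrolled woman a fit failure. With no fit failures the difference disappears.

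The calculation for the supervised test assumes that Section 5.2 is applied as written; the home-use figures also count fit failures as non-successes. The endpoint is exploratory and descriptive and the primary analysis is untouched, so this is a worthwhile improvement and not a threat to the study's main conclusion.

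**What to change.** In the SAP, to which Section 10.6 defers these details:

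1. Define successful use and state whether it is judged at the supervised test, over home use, or both.
2. Report supervised insertion and removal success in all women who attempted self-insertion at screening, with exact confidence intervals. Tabulate reasons for failure separately: instruction or insertion error, poor fit, comfort, voiding.
3. In the same women, cross-tabulate self-assessed fit against the physician's verdict and report agreement with an exact interval.
4. Make sure these results are recorded in analysable form for screen failures; the documents do not confirm that they are.
5. Report home use separately among women given devices.

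In the protocol, reconcile Section 5.2 (exclusion) with Section 7.3 (discretionary termination). Also reconcile the timing in Section 2.2 (enrollment) with the Schematic and Section 7.3 (screening).

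The cost is one extra table, some attention to screen-failure records, and possibly a less favourable figure. The new denominator does not remove the physician's presence, so the result would still describe supervised use.
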